## **3.1.3. Study Endpoints**

The endpoints for the study include the following:

- Pharmacokinetic Parameters**

Cycle 1/Days 1 and 2 (Part 1 and Part 2):

- Maximum (peak) plasma concentration (Cmax), time to reach maximum plasma concentration (Tmax), area under the plasma concentration-time curve up to the last quantifiable time (AUClast)
- If appropriate: Area under the plasma concentration-time curve up to infinity (AUCinf), terminal elimination half-life (t1/2), apparent total body clearance

following a single dose administration (Cycle 1/Day 1) (CL/F), apparent volume of distribution based on the terminal phase (Vz/F)

Cycle 1/Day 8 (Part 1 and Part 2):

- Cmax, Tmax, AUClast, and comparison of Cmax and AUClast values between Day 8 and Day 1 (Cmax and AUClast ratio) (d8,d1)
- If appropriate: Area under the plasma concentration-time curve during dosing interval (AUCtau), AUCinf, t1/2, apparent total body clearance at steady state following multiple dose administration (Cycle 1/Day 8) (CLss/F), apparent volume of distribution at steady state after multiple-dose administration (Vss/F)

Cycle 1/Days 2, 8, 15, and 22 and Cycle 2/Day 1 (Part 1 and Part 2):

- Trough plasma concentration (Ctrough)

End-of-treatment (EOT) (Part 1 and Part 2):

- Ctrough

- **Exploratory Biomarker Parameters**

- Exploratory molecular testing in blood cells and/or bone marrow cells (at pre-dose and post-dose time points)
- Retrospective confirmatory analysis and correlation with pre-therapy cytogenetic and molecular subsets of AML or ALL to response

- **Pharmacodynamic Parameters**

- Quantitation of leukemic stem cells in pre- and post-dose bone marrow cells by flow cytometry and/or mass cytometry
- H3K27me3 status in leukemic stem cells in bone marrow and/or blood cells

- **Efficacy Parameters**

Primary efficacy variable is response to treatment, which will be defined per the revised IWG response criteria for AML or standard response criteria for ALL as defined in Appendix Section 17.3 (NCCN 2016 ALL response criteria).

The efficacy endpoints will be:

- Composite complete remission (CRc) rate, including complete remission (CR), complete remission with incomplete blood count recovery (CRI), and CRp
- Morphologic leukemia-free state (MLFS)
- Partial remission (PR) rate
- Overall response rate (ORR) = CRc+PR

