### **3.1.8. Maximum Tolerated Dose and Recommended Dose for Expansion Definition**

Once the stopping criteria are met, the MTD estimated by BLRM + EWOC is the dose with the highest posterior probability of the DLT rate in the target DLT rate interval of [16%, 33%] among all doses fulfilling the following 2 constraints:

- The overdose control constraint: There is less than a 25% probability for the DLT rate  $>33\%$  (probability for excessive or unacceptable toxicity) (Section 3.1.2.1);
- The mean of the posterior distribution of DLT target rate at this dose is  $\leq 25\%$ .

Since an alternative drug administration schedule may be explored in lieu of or in parallel with the original QD  $\times$  28/28 days schedule, separate MTDs may be identified for each regimen. The final MTD for each dosing schedule will be decided based on considerations of the respective MTDs estimated by the BLRM and on an overall assessment of safety data from subsequent cycles and PK/PDy response information collected at all different doses tested. Upon determining the final MTD of the original QD  $\times$  28/28 days and/or alternative dosing schedules, 1 dosing regimen will be selected for further evaluation in Part 2 (Dose Expansion). This regimen given at the final MTD determined in Part 1 is referred to as the “Tentative Recommended Dose for Expansion”.

In the Dose Expansion cohort, the safety will be assessed continuously after 4 subjects are enrolled in each cohort of AML and ALL. The study will be stopped if the cumulative incidence of clinically relevant  $\geq$ Grade 3 toxicities exceed 30%. The exceptions are:

- Grade 3 and higher nausea, vomiting, or diarrhea that do not require hospitalization or TPN support and can be managed with supportive care to  $\leq$ Grade 2 within 48 hours.

- Alopecia and study drug-related fever.
- Grade 3 or 4 electrolyte abnormalities that are corrected to  $\leq$ Grade 2 within 24 hours.
- Grade 3 or 4 differentiation syndrome which improves to  $\leq$  Grade 1 within 7 days of the start date of  $\geq$  Grade 3 differentiation syndrome and which is not associated with end-organ damage.

Evaluation of myelosuppression will be decided between the Investigators and Sponsor Medical Monitor during safety review meetings.

In the Dose Expansion cohort, the efficacy will be assessed continuously after 10 subjects are enrolled. The study will be stopped if the cumulative ORR will be less than 10%.

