#### **4.2. Removal of Subjects from Therapy**

A subject may withdraw from receiving study drug treatment (but remain available for follow-up) or withdraw completely from all study participation at any time. For subjects with AML, therapy will be discontinued if there is a lack of leukemic response (ie, CR, CRi, CRp, or PR) after 3 cycles of therapy, unless the Investigator has determined that the subject is deriving

clinically benefit from treatment. For subjects with ALL, therapy will be discontinued if there is progressive disease per NCCN. Subjects with persistent bone marrow aplasia lasting more than 4 weeks, as per institutional guidelines, in the absence of malignant cell infiltration >4 weeks and peripheral ANC  $<0.5 \times 10^9/L$  and platelets  $<20 \times 10^9/L$ , will also be discontinued from therapy.

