## 7. EFFICACY ASSESSMENTS

Efficacy assessments will be based on bone marrow assessments to be performed at Screening, Cycle 1 Day 8, and every cycle of treatment (ie, at start of Cycles 2, 3, 4, etc.) while the subject remains on study drug. The clinical activity of DS-3201b will be assessed using the revised IWG response criteria for AML or the NCCN Guidelines (Version 3.2013) for ALL (Section 17.3).

The efficacy endpoints will be:

- CRc rate (CR, CRi, and CRp)
- CR
- CRi or CRp
- MLFS
- PR rate
- ORR = CRc+PR
- DOR: Time from the first objective evidence of response to the first objective evidence of disease progression
- OS: Time from the date of enrollment to the date of death from any cause
- 30- and 60-day mortality rate

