#### **11.1.3. Full Analysis Set**

The Full Analysis Set will include all subjects enrolled in the Dose Escalation part or the Dose Expansion part who received any amount of DS-3201b and who had at least 1 post-baseline bone marrow assessment.

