## 11.10. Sample Size Determination

The Dose Escalation part of the study will enroll 3 to 6 subjects in each cohort, based on a BLRM under the EWOC principle. It is possible that a dose level may enroll more than one cohort based on the BLRM recommendation. The number of subjects enrolled depends on the observed DLTs, but it is expected that 21 or more subjects might be enrolled in the Dose Escalation part.

For the Dose Expansion part, additional subjects will be enrolled at the RDE dose level as suggested based on data in the Dose Escalation part. Approximately 20 subjects each with AML and ALL will be enrolled at the RDE dose level, including those dosed at the same dose level in the Dose Escalation part, which is expected to number between 6 and 9. The size of 40 is deemed to be sufficient for the assessment of safety and tolerability, as well as the clinical antitumor activity. Assuming a true CRc rate of 20%, the probability of observing 3 or more CRc among the 20 subjects is 79.4% for AML and ALL, respectively.

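### The Part 2 futility looks start at 10 enrolments with no minimum follow-up, so an active drug is stopped more often than the same rule would stop it on mature data

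*Combined protocol and SAP*

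**What the plan says.** Section 3.1.8 states: "In the Dose Expansion cohort, the efficacy will be assessed continuously after 10 subjects are enrolled". It then states: "The study will be stopped if the cumulative ORR will be less than 10" (per cent). The stop is worded as mandatory. Section 3.1.3 defines the measure: "Overall response rate (ORR) = CRc+PR".

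Other sections bear on when a response can be known:

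- **Enrolment.** Section 4.1 counts a subject as enrolled on consent plus confirmed eligibility, which precedes dosing.
- **Assessment times.** Section 7 bases efficacy on "bone marrow assessments to be performed at Screening, Cycle 1 Day 8, and every cycle of treatment", with 28-day cycles.
- **Time to respond.** For AML, Section 4.2 says "therapy will be discontinued if there is a lack of leukemic response (ie, CR, CRi, CRp, or PR) after 3 cycles of therapy". It makes an exception where the investigator sees clinical benefit. For ALL, the same section ties discontinuation to progression. The ALL criteria in Section 17.3.2 require 4 weeks without recurrence for a CR.
- **Analysis set.** Section 11.2 analyses efficacy on the Full Analysis Set, which Section 11.1.3 limits to treated subjects "who had at least 1 post-baseline bone marrow assessment".
- **Lead-in.** Section 3.1.2.2 requires 4 subjects per disease to complete the Cycle 1 safety evaluation before the rest of that cohort enrols.
- **Cohort size.** Section 11.10: "Approximately 20 subjects each with AML and ALL will be enrolled at the RDE dose level". This includes the 6 to 9 subjects expected at that dose from Part 1.

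Section 3.1.8 does not say which subjects form the ORR denominator, how long they must have been followed, whether the 10 are per disease or pooled, or whether Part 1 subjects count. Section 11.8 plans no formal interim analysis beyond the MTD assessment. No operating characteristics are given for the rule.

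**The concern.** The trigger is enrolment but the quantity tested is response, and response takes one or more cycles to document. At the 10th enrolment that subject has no follow-up at all, and others may have only days or weeks. A subject who will respond but has not reached the marrow that shows it adds nothing to the numerator. Cumulative ORR at each look is therefore biased downward, and more so the faster the cohort fills.

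A false stop would cost Part 2 its ORR, DOR and OS objectives for a drug with the activity assumed in Section 11.10.

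**Working it through.** **1. The plan's own figure.** Section 11.10 states: "Assuming a true CRc rate of 20%, the probability of observing 3 or more CRc among the 20 subjects is 79.4" (per cent). Check: 1 − [0.8^20 + 20(0.2)(0.8^19) + 190(0.04)(0.8^18)] = 1 − (0.0115 + 0.0576 + 0.1369) = 0.794. It reproduces. It is a CRc figure; ORR also includes PR, so 20% is a floor for ORR under the plan's assumption.

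**2. The boundary.** With k responders among n, the study stops if k/n < 0.10. At n = 10 this means k = 0. At n = 11 to 20 it means k ≤ 1, since 1/11 = 9.1% and 2/20 = 10%.

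**3. Benchmark with every subject mature.** First look at ORR 20%: 0.8^10 = 0.107. For looks after each subject from 10 to 20, a cohort stops unless it has 2 responses among its first 11: 0.8^11 + 11(0.2)(0.8^10) = 0.0859 + 0.2362 = 0.322. At ORR 30% the two values are 0.028 and 0.113.

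**4. First look with immature subjects.** The denominator D is at most 10, so one documented response gives at least 10% and zero gives 0% whatever D is. The first look therefore stops exactly when no response has been documented, under either denominator. If m of the 10 have passed the point at which a response would show, the probability at ORR 20% is 0.8^m:

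| m | P(stop at first look) |
|---|---|
| 10 | 0.107 |
| 8 | 0.168 |
| 6 | 0.262 |
| 4 | 0.410 |

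The lead-in guarantees m = 4 only if responses show by the end of Cycle 1.

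**5. Simulation over accrual.** These inputs are assumptions, because the documents give neither accrual nor time to response:

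- 1, 2 or 4 subjects per 28 days per disease, with exponential gaps
- a 28-day pause after subject 4
- 20 subjects per disease and no Part 1 subjects counted
- true ORR 20%
- looks at each enrolment from 10 to 20
- response documented either at day 28 or with equal chance at days 28, 56 and 84
- Full Analysis Set entry at the Cycle 1/Day 8 marrow

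On average 8.0, 7.0 and 5.4 of the first 10 subjects have passed day 28 at the first look.

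| P(stop), ORR 20% | 1 per 28 d | 2 per 28 d | 4 per 28 d | Mature |
|---|---|---|---|---|
| First look, days 28/56/84 | 21% | 30% | 48% | 10.7% |
| First look, day 28 | 17% | 21% | 32% | 10.7% |
| Any look, days 28/56/84, all enrolled | 51% | 65% | 81% | 32% |
| Any look, days 28/56/84, Full Analysis Set | 44% | 57% | 73% | 32% |
| Any look, day 28, all enrolled | 44% | 52% | 66% | 32% |
| Any look, day 28, Full Analysis Set | 37% | 43% | 54% | 32% |

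Repeat runs differ by 1 to 2 percentage points. At ORR 30%, with spread responses and all enrolled subjects counted, the any-look figures are 28%, 42% and 65%, against 11% mature.

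**The case against.** A reader might infer that none of the analysed subjects can have reached a response assessment. The documents do not support that: the lead-in means at least 4 of the first 10 in a disease cohort have completed Cycle 1, and there is a Day 8 marrow. Leaving out the lead-in pause would give about 60% at the first look and 87% at any look for accrual of 4 per month, which overstates the problem.

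A reader might also infer that the plan counts immature subjects as non-responders. No section says so. The denominator is undefined, and the Full Analysis Set reading drops subjects with no post-baseline marrow. That lowers the later-look figures but not the first-look ones (step 4), and the Day 8 marrow admits subjects after about a week of drug.

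Nor can it be said that the rule mainly measures accrual speed. With accrual of 1 per 28 days, responses at day 28 and the Full Analysis Set, the excess is only 37% − 32% = 5 percentage points. If mature Part 1 subjects count, the excess also shrinks. With an assumed 3 per disease, spread responses and accrual of 4 per month, the first-look figure is about 34% and the any-look figure about 70% (62% on the Full Analysis Set). Section 3.1.8 does not say that they count.

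These objections limit the size. They leave standing that the rule is mandatory and has no follow-up requirement.

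**Conclusion.** The point holds. The rule as written stops an active drug more often than the same rule on mature data in every setting examined, and the excess grows with accrual speed and time to response. At a true ORR of 20%, the first-look probability rises from 10.7% to between 17% and 48%, and the any-look probability from 32% to between 37% and 81%. The direction follows from the text. The size rests on assumed accrual and response timing, on reading the 10 as per disease, and on not counting Part 1 subjects.

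The 32% on mature data comes from the boundary and the repeated looks. It should not be attributed to immature follow-up.

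**What to change.** In Section 3.1.8, replace the enrolment trigger with follow-up maturity. For example: after the first 10 treated subjects, taken in order of first dose, have each reached a fixed response-assessment time point or stopped treatment or died before it; at each look ORR is computed only on subjects whose first dose was at least that long ago, responders and non-responders alike. Subjects who stopped or died early then enter the denominator on the date their time point would have fallen, with whatever response they had.

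The equal treatment matters. Counting early responders at once while non-responders wait three cycles biases ORR upward. Any-look stopping at ORR 20% would fall to 11–29% against 32% mature, and stopping at a 5% ORR could fall to 77% against 90%.

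The sponsor should also:

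- set the time point for each disease from its own assessment schedule, since three cycles is stated for AML only and the ALL criteria in Section 17.3.2 need separate thought
- state whether the 10 are per disease or pooled
- state whether Part 1 subjects at the RDE count
- report the rule's operating characteristics.

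**Cost.** The first look comes later. Expected enrolment by then is about 10 + rate × (window/28), capped at 20. For an 84-day window this is 10 + 3 = 13, 10 + 6 = 16, and about 19 of 20 at the fastest rate, where the cap binds. The rule then saves few subjects when accrual is fast. A shorter window reduces this: at 28 days the figures are 11, 12 and 14. The price is that later responses are missed. The change removes only the immaturity excess; the 32% remains for separate consideration.

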### **3.1.9. Management of Subjects with Adverse Events**

Treatment-related toxicities meeting the DLT definition (see Section 3.1.7.2 for DLT definitions) occurring during the study will result in interruption and/or discontinuation of therapy. For subjects deriving clinical benefit from treatment, an option to resume the therapy at 1 dose level below that at which the toxicity occurred may be considered after the toxicity returns to NCI-CTCAE  $\leq$ Grade 1 or to baseline values. However, subjects requiring more than 4 weeks to recover from acute toxicities will be withdrawn from treatment. If a subject experiences NCI-CTCAE Grade 3 or 4 toxicity or an SAE that is unequivocally attributable to the underlying malignancy, DS-3201b treatment may be postponed until the toxicity has resolved to NCI-CTCAE  $\leq$ Grade 1, or returns to baseline values.

### **3.1.10. Guidelines for Dose Delays**

Dosing of DS-3201b should be interrupted if the following AEs develop at any time during treatment:

- NCI-CTCAE  $\geq$ Grade 2 non-hematological, non-disease-related toxicities, except alopecia and  $>$ Grade 2 fatigue lasting  $<$ 48 hours.
- For other NCI-CTCAE  $\geq$ Grade 2 laboratory abnormalities that are not DLTs, treatment continuation with DS-3201b will be at the discretion of the Investigator.
- Bone marrow aplasia, as per institutional guidelines, and peripheral ANC  $<0.5 \times 10^9/L$  and platelets  $<20 \times 10^9/L$ , with no residual leukemia.

Commencing rules for DS-3201b administration after dose interruption due to hematological AEs are:

- ANC  $\geq 0.5 \times 10^9/L$ .
- Platelet count  $\geq 20 \times 10^9/L$ .
- All other NCI-CTCAE  $\geq$ Grade 2 non-hematological toxicities (excluding alopecia) must have resolved to  $\leq$ Grade 1 or baseline values.

These parameters are only guidelines and are not intended to supersede the clinical judgment of the treating physician. All adjustments should be made in consultation with the Sponsor Medical Monitor. In the event of a dose delay occurring prior to completion of the PK/PDy sampling in

the study, Investigators should contact DSI for guidance regarding rescheduling these procedures.

In the event of a dose delay due to noncompliance, the study site should notify DSI at the earliest possible time. Subjects missing more than 25% of scheduled doses in Cycle 1 for non-toxicity-related reasons will not be evaluable for DLT and may be removed from the study.

## **3.2. Selection of Doses**

### **3.2.1. Experimental Treatments**

In this Phase 1, non-randomized, open-label study, each subject will be administered DS-3201b orally once daily over a 28-day cycle (1 Cycle). In the first cohort, study treatment initiation will be staggered. A delay of at least 7 days will occur between the first subject dosed and the second and third subjects dosed. In subsequent cohorts, the study treatment can be started in the second and third subjects 1 day after first administration in the first subject.

The starting dose will be 100 mg once a day. The dose will be administered without food (no food for at least 2 hours before and 1 hour after the dose). A missed dose of DS-3201b may be administered later that same day (until midnight). The dose will be assessed as a missed dose if not administered. No replacement dose is administered if the subject vomits after taking DS-3201b.

#### **3.2.1.1. Part 1 (Dose Escalation)**

The study will enroll subjects into cohorts with dose escalation determined by BLRM with the EWOC principle as outlined in Section 3.1.2.1. The starting dose will be 100 mg/day (see Section 3.1.2.1 for justification of the starting dose). In the event of a DLT, the next 2 subjects will receive DS-3201b treatment starting at least 1 week apart.

#### **3.2.1.2. Part 2 (Dose Expansion)**

Upon completion of Part 1 (Dose Escalation) and determination of the MTD/RDE, Part 2 (Dose Expansion) will immediately begin. Subjects will receive DS-3201b at the MTD/RDE defined in Section 3.1.2.1.

### **3.2.2. Control Treatments**

Not applicable.

### **3.2.3. DS-3201b Dose Reduction Guidelines**

The dose of DS-3201b will be reduced when concomitant strong CYP3A and/or P-gp inhibitors are co-administered (Table 3.1). When the strong CYP3A and/or P-gp inhibitors are discontinued, the subject will remain on the reduced dose for 3 days after the last dose of the inhibitor(s). After 3 days, the DS-3201b dose may be returned to the dose level that the subject was given before taking the inhibitor(s).

During this period of co-administration of moderate or strong CYP3A and/or P-gp inhibitors with DS-3201b, additional blood samples for PK analyses (total and unbound concentrations) should be collected (see Section 8 for additional details).

A list of CYP3A inhibitors/inducers and P-gp inhibitors is presented in Section 17.5.

**Table 3.1: Criteria for Dose Reduction When Using Strong CYP3A Inhibitors and/or P-gp Inhibitors**

Drugs to be Co-administered with Care	Dose Adjustment Guideline	Examples of the dose reduction		
		When the Dose of the Study Drug is 500 mg Once Daily	When the Dose of the Study Drug is 250 mg Once Daily a	When the Dose of the Study Drug is 150 mg or 100 mg Once Daily a
Strong CYP3A inhibitors	Reduce DS-3201b dose to 50%	Reduce the dose of the study drug to 250 mg once daily	Reduce the dose of the study drug to 100 mg once daily	Reduce the dose of the study drug to 50 mg once daily
P-gp inhibitors	Reduce DS-3201b dose to 50%	Reduce the dose of the study drug to 250 mg once daily	Reduce the dose of the study drug to 100 mg once daily	Reduce the dose of the study drug to 50 mg once daily
Drugs having a strong CYP3A inhibitory effect and a P-gp inhibitory effect	Reduce DS-3201b dose to 25%	Reduce the dose of the study drug to 100 mg once daily	Reduce the dose of the study drug to 50 mg once daily	Interrupt the study drug

CYP3A = cytochrome P450 3A; P-gp = P-glycoprotein

a When the dose of study drug is 250 mg, 150 mg or 100 mg once daily, the Investigator should consult the Sponsor Medical Monitor before further reduction of the dose due to concomitant use of strong CYP3A or/and P-gp inhibitors

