#### **1.4.3. Potential Risk of Drug-Drug Interaction**

In vitro, DS-3201a was metabolized extensively by CYP3A4 (approximately 66%) and CYP3A5 (approximately 30%), and to a lesser extent also by CYP2C8 (approximately 16%). The results of the in vitro study showed that DS-3201a is a substrate for P-gp. Drugs that are moderate-to-strong inducers of CYP3A4 may alter the PK of DS-3201a.

Study DS-3201-A-J104 demonstrated that the co-administration of itraconazole, a dual P-gp and strong CYP3A inhibitor, resulted in an approximately 4-fold increase in the AUCs and an approximately 3-fold increase in Cmax of DS-3201a. The co-administration of DS-3201b and the moderate CYP3A inhibitor fluconazole resulted in a 1.6-fold increase in the Cmax and AUCs of DS-3201a.

Additionally, the results of the DS3201-A-J104 study investigating drug interactions with CYP3A inhibitors and physiologically-based pharmacokinetic (PBPK) modeling analyses predicted that the combination of a single dose of DS-3201b and a strong CYP3A and P-gp inhibitor would increase the AUC of DS-3201a by approximately 4-fold, and a strong CYP3A inhibitor (no P-gp inhibitory effect) or a P-gp inhibitor (no CYP3A inhibitory effect) would

increase the AUC of DS-3201a by approximately 2-fold, respectively. If strong CYP3A inhibitors and/or P-gp inhibitors are co-administered, the dose adjustment guidance provided in [Table 3.1](#) must be followed. The increase in AUC of DS-3201a was less significant when DS-3201b was concomitantly administered with a moderate CYP3A4 inhibitor. Therefore, no dose reduction of DS-3201b is required when it is concomitantly administered with a moderate CYP3A inhibitor.

DS-3201a inhibited CYP3A4 (tested with midazolam,  $IC_{50}$  55.2  $\mu$ M) but did not directly inhibit CYP1A2, CYP2B6, CYP2C8, CYP2C9, CYP2C19, CYP2D6, or testosterone metabolism by CYP3A4. The potential DS-3201a inhibition on CYP3A4 (midazolam) was confirmed by subsequent determination of a  $K_i$  of 56.4  $\mu$ M. DS-3201a showed a tendency to be a metabolism-dependent inhibitor of CYP3A4, with an  $IC_{50}$  fold change of 7.8-fold. Determination of  $k_{inact}/K_i$  inactivation constants suggested that DS-3201a is not a potential CYP3A4 metabolism-dependent inhibitor, since the inactivation constants were not measurable. DS-3201a did not show metabolism-dependent inhibition of any other CYPs tested.

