### **1.5. Population, Route, Dosage, Dosage Regimen, Treatment Period**

DS-3201b is supplied as 25 mg and 100 mg capsules packaged in high-density polyethylene (HDPE) bottles. DS-3201b will be administered orally at a starting dose of 100 mg once a day until disease progression.

See [Section 3.1](#) for a detailed description of the study drug administration schedule, treatment cycle duration, and follow-up after discontinuation.

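### Table 3.1 states reductions to 50% or 25% of dose, but 8 of its 12 row-by-dose examples differ from that rule, and nothing says which column governs

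*Combined protocol and SAP*

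**What the plan says.** Section 3.2.3 requires a lower dose of study drug while strong CYP3A and/or P-gp inhibitors are given, and refers to Table 3.1. Section 1.4.3 makes this mandatory: when such drugs are co-administered, "the dose adjustment guidance provided in" Table 3.1 must be followed.

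The table has a guideline column and three example columns (500 mg; 250 mg; 150 or 100 mg).

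- Strong CYP3A inhibitors, and separately P-gp inhibitors: "Reduce DS-3201b dose to 50" per cent. The examples are "Reduce the dose of the study drug to 250 mg once daily" from 500 mg, "Reduce the dose of the study drug to 100 mg once daily" from 250 mg, and "Reduce the dose of the study drug to 50 mg once daily" from 150 or 100 mg.
- Drugs with both effects: "Reduce DS-3201b dose to 25" per cent. The examples are 100 mg from 500 mg, 50 mg from 250 mg, and "Interrupt the study drug" from 150 or 100 mg.

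Footnote a is attached to the 250 mg and the 150/100 mg columns and calls for consultation with the Sponsor Medical Monitor. It is not attached to the 500 mg column. On formulation, Section 1.5 says "DS-3201b is supplied as 25 mg and 100 mg capsules", and Section 5.1 repeats this.

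**The concern.** An example should show the rule at work. Here most examples contradict it, in a table that must be followed, and the table does not say whether the percentage or the example prevails. No rounding rule is given.

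Two subjects at the same assigned dose, taking the same class of inhibitor, could therefore receive different reduced doses, each defensible from the table. Section 5.2.1 permits these inhibitors during the study where they are needed, for example in connection with infection. Section 11.5.1 summarises PK by dose level and Section 11.6 tabulates DLTs by dose level, so an unresolved instruction may add avoidable exposure spread to data meant to characterise dose.

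**Working it through.** **Inputs.** Percentages, example doses and footnote: Table 3.1. Capsule strengths of 25 mg and 100 mg: Sections 1.5 and 5.1. Approximate AUC rise, 2-fold for a strong CYP3A inhibitor alone or a P-gp inhibitor alone and 4-fold for both effects: Section 1.4.3.

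**Formulas.** Rule dose = starting dose × 0.50 or × 0.25. Example fraction = example dose ÷ starting dose. A rule dose can be made from the capsules if it is a multiple of 25 mg. Relative exposure = example fraction × AUC multiplier, assuming dose-proportional exposure. Three rows by four starting doses give 12 combinations; the two 50% rows are identical.

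| Row | Start (mg) | Rule dose (mg) | Example (mg) | Example fraction | Rule dose makeable? | Relative exposure under example | Footnote a? |
|---|---|---|---|---|---|---|---|
| 50% (two rows) | 500 | 250 | 250 | 50% | yes | 2 × 0.50 = 1.00 | no |
| 50% (two rows) | 250 | 125 | 100 | 40% | yes | 2 × 0.40 = 0.80 | yes |
| 50% (two rows) | 150 | 75 | 50 | 33.3% | yes | 2 × 0.333 = 0.67 | yes |
| 50% (two rows) | 100 | 50 | 50 | 50% | yes | 2 × 0.50 = 1.00 | yes |
| 25% | 500 | 125 | 100 | 20% | yes | 4 × 0.20 = 0.80 | no |
| 25% | 250 | 62.5 | 50 | 20% | no | 4 × 0.20 = 0.80 | yes |
| 25% | 150 | 37.5 | interrupt | 0% | no | 0 | yes |
| 25% | 100 | 25 | interrupt | 0% | yes | 0 | yes |

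The rule doses are arithmetic from the stated percentages, not a recommendation.

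**Count.** Matches: 500 to 250 and 100 to 50, each in two rows, so 4 of 12. Numeric mismatches: 2 + 2 + 1 + 1 = 6 (four distinct pairs if the two identical rows are merged). Interruptions: 2. Total differing from the rule: 6 + 2 = 8 of 12.

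**Capsule rounding.** Only 62.5 mg and 37.5 mg cannot be made. The rule doses of 125, 75 and 25 mg can, so capsule strength does not account for 250 to 100, 150 to 50, 500 to 100, or interruption at 100 mg.

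**Exposure.** Under the percentages, relative exposure is 2 × 0.50 = 1.00 or 4 × 0.25 = 1.00. Under the mismatched numeric examples it is 0.80 or 0.67, a shortfall of 20% or 33%.

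**Doses with no example.** Section 11.11.3 also lists 350, 700 and possibly 1000 mg. The table has no example there, so only the percentage applies: 350 mg would follow 50% while 250 mg follows 40%. At 350 mg with a dual-effect drug, 0.25 × 350 = 87.5 mg, which again cannot be made and again has no rounding rule.

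**The case against.** The strongest reply is that the second set of columns contains explicit instructions, one per listed dose, and that every mismatched example lies below the percentage dose, as deliberate rounding down would. That may be the intent, but the table does not say so, and rounding to available capsules accounts for few of the cells.

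Footnote a is a real safeguard. Five of the six numeric mismatches, and both interruptions, fall in columns it covers, so a reader who infers that sites choose a column unaided goes too far. What stands is narrower. The footnote names no governing column, its wording leaves open whether it covers the first reduction or only a later one, and it does not reach 500 mg with a dual-effect drug, where 25% is 125 mg and the example says 100 mg.

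A reader might also infer that dose-reduced subjects still count at their cohort dose in the DLT model and so distort the MTD. The documents do not say this. Section 11.1.2 summarises the Safety Analysis Set by dose received. Section 11.1.4 defines DLT evaluability by the share of scheduled doses taken and is silent on inhibitor-driven reductions. Strong CYP3A inhibitors are excluded within 7 days of the first dose (Section 4.1.2), and Sections 3.2.3 and 8 call for extra total and unbound PK samples during co-administration, so exposure in these subjects is meant to be measured.

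Finally, moving from 80% to 100% of nominal exposure is a step of 1 ÷ 0.80 = 1.25, or 25%, below the 30% minimum dose increment that Section 3.1.2.1 sets to distinguish dose levels given variability in exposure. Only 150 to 50 mg exceeds that mark (1 ÷ 0.667 = 1.5, or 50%) among the numeric examples. This is a fair reason not to exaggerate the effect, but it does not make the two columns agree.

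**Conclusion.** The point holds as an internal contradiction in a mandatory dosing table: 8 of 12 combinations depart from the stated percentage, six of them by a different numeric dose. The clearest case is 500 mg with a dual-effect inhibitor, because the percentage dose can be made from the capsules and no footnote applies.

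The exposure figures (about 100% under the percentages; about 80% or 67% under the mismatched numeric examples) assume dose-proportional exposure in humans and take at face value AUC multipliers that Section 1.4.3 gives as approximate and, for the class-wide figures, predicts for a single dose. Under those assumptions neither column takes predicted AUC above nominal. The effect on dose finding cannot be sized, because the documents give neither the frequency of co-administration nor the dose level at which such subjects enter the DLT model. The correction should be made, but the documents do not support a claim that the MTD estimate is biased.

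**What to change.** Reconcile the percentage and example columns of Table 3.1 so that each starting dose and inhibitor class leads to one instruction. State which column governs, give any rounding rule, and say what applies at provisional doses with no example. State whether the footnoted consultation covers the first reduction, and how 500 mg is to be handled. Which dose is right is for the sponsor's clinical team; no view is taken here.

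The cost is the correction of one table and a notice to sites. Data already collected do not need to be recoded for this change.
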